**Title: Effect of Sport Education in University Required PE on Students'
Perceived Physical Literacy and Physical Activity Level**

NCT number: NCT03888885

Date: 12/9/2021

Study Protocol

Research design

This study employed a 10-lesson cluster-randomized study design to examine the effect of sport education on domains of student PL and physical activity levels. Questionnaires, accelerometers, and video recordings of PE lessons were used to collect self-report and objective data measures.

[figure not shown]
Eligibility and randomization

Only one university in Hong Kong fully funded by the University Grants Committee and requires the completion of two semesters of PE coursework for graduation. Lecturers in the PE program are required to have a master's degree or above and have more than 5 years of teaching experience. All lecturers attended a 12-h continuous professional development workshop on sport education. Of the 25 lecturers who attended the workshop, 11 of them consented to participate in the study. The required sample size of students was calculated based on the hypothesized effect sizes and the likely rates of participants dropout for outcome measures. A total number of 2886 students were admitted to the university in the academic year, with an estimated required cluster sample size of 341 with an effect size of 0.25, α of 0.05, and a power of 0.95 (Faul et al. 2007). In anticipation of 10–20% of the dropout rate across data collection phases, this led to a required number of 8 classes for each of the sport education and traditional groups. PE classes were initially grouped by lecturers and types of sports (individual sports, team sports, and physical conditioning) and then randomly assigned to each intervention (Fig. 1) by a computer-generated sequence (GraphPad Software, Inc.) conducted by a statistician who was blind to the purposes of the study. The demographic background and corresponding courses for each of the eight lecturers are shown in Table 1. Students were eligible to participate in the study if they were aged 18 or above and indicated all negative statements in the self-screening Physical Activity Readiness Questionnaire (Thomas et al. 1992) which can uncover heart, circulatory, balance, medication, emotional, and joint problems that could make exercise difficult or dangerous for some people. Written consent for study participation was also obtained.

PE curriculum intervention

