Situational motivation scale (SIMS) The SIMS is a 16-item instrument that was used to measure participants' situational intrinsic and extrinsic motivation while performing given physical activities. The four behavioral subscales include intrinsic motivation, identified regulation, external regulation, and amotivation (Deci et al. 1991). Participants responded to the instrument on a 7-point Likert scale (1 = not at all true and 7 = very true). Example items include the following: (a) this activity is fun (intrinsic motivation); (b) I believe this activity is important for me (identified regulation); (c) I do not have any choice (external regulation); and (d) I do this activity, but I am not sure it is a good thing to pursue it (amotivation). Guay et al. (2000) reported adequate internal consistency ($\alpha = 0.77$ – 0.95) and construct validity in physical activity settings among college-aged students.

Physical activity enjoyment scale (PACES) PACES is a survey instrument that measures how much a student enjoys participating in physical activity. Participants responded to the 16-item instrument on a 5-point Likert scale (1 = disagree a lot and 5 = agree a lot). There are nine positive items such as "I find it pleasurable" and "It gives me energy" and seven negative items such as "I dislike it" and "It is not fun at all." Participants who receive high scores on positive items and low scores on negative items would indicate a high enjoyment of the physical activity. Motl et al. (2001) established adequate internal consistency ($\alpha = 0.81$ – 0.86) and factorial and construct validity of PACES with college-aged students.

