**Title: Effect of Sport Education in University Required PE on Students'
Perceived Physical Literacy and Physical Activity Level**

NCT number: NCT03888885

Date: 12/9/2021

Statistical Analysis Plan

ActiLife 6 software (ActiGraph LLC), a designated software for transferring data from accelerometers to computers, was used to transfer physical activity data with a metabolic cut point of Freedson et al. (1998). IBM SPSS statistics version 22 for Windows (IBM SPSS) was used for all data analysis (Field 2009). One-way analyses of variance (ANOVAs) were used to assess differences between groups in the baseline measures of demographic information, each outcome measure, as well as the mean percentage of physical activity levels, lesson context, and teacher involvement during PE lessons. Pearson's correlation was used to compute the association between self-report and objective physical activity levels. To evaluate the effect of the different types of curriculum interventions on outcome measures, a series of repeated-measures multivariate analysis of variance (MANOVAs) were used with time (baseline, post-intervention, and follow-up) as the within-subjects factor and group (intervention group and control group) as the between-subjects factors. MANOVA analyses are the most appropriate analyses to discern differences between groups over time and to establish any potential group by time interaction effects (Tabachnick and Fidell 2014). Specifically, MANOVA is likely to prevent type I error when dependent outcomes may be correlated and thus potentially share some of the same variances. Post hoc Scheffe analyses were conducted to determine contributing factors to significant MANOVA F values. The significance level was set at 95% for all analyses.

References

Field, A. (2009). *Discovering statistics using SPSS*. London: SAGE Publications Ltd.

Freedson, P. S., Melanson, E., & Sirard, J. (1998). Calibration of the computer science and applications, inc. accelerometer. *Medicine and Science in Sports and Exercise*, 30(5), 777–781.

Tabachnick, B. G., & Fidell, L. S. (2014). *Using multivariate statistics*. Harlow: Pearson Education Limited.

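### As specified, the Scheffé follow-up does not identify which outcomes changed differently between the arms

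*SAP*

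**What the plan says.** The Protocol (Research design) sets out "to examine the effect of sport education on domains of student PL and physical activity levels". For the effect on outcomes, the SAP specifies "a series of repeated-measures multivariate analysis of variance (MANOVAs) were used with time (baseline, post-intervention, and follow-up) as the within-subjects factor". The second factor in the model has two levels: "group (intervention group and control group) as the between-subjects factors". One stated purpose is "to establish any potential group by time interaction effects". The stated ground for error control is that "MANOVA is likely to prevent type I error when dependent outcomes may be correlated".

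The only follow-up is this sentence: "Post hoc Scheffe analyses were conducted to determine contributing factors to significant MANOVA F values". The SAP does not say which means or contrasts Scheffé compares, or which outcomes form a family. It does not list the MANOVAs or their dependent variables, and it uses one significance level throughout. The Protocol adds nothing on follow-up tests.

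Two facts in the Protocol bear on this. Several instruments have subscales: for the SIMS, "The four behavioral subscales include intrinsic motivation, identified regulation, external regulation, and amotivation", and the PPLI has three. Allocation was by PE class, with a "required number of 8 classes for each of the sport education and traditional groups" (Eligibility and randomization), whereas the SAP model contains group and time only.

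**The concern.** The aim concerns domains of physical literacy and physical activity, so conclusions will be drawn subscale by subscale. A significant multivariate group-by-time test says only that something in the set of outcomes changed differently between arms. The follow-up has to say what.

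Scheffé is a procedure for contrasts among the levels of a factor. The SAP names two factors, and a post hoc on either one does not address the between-arm difference in change. If the factors meant in the follow-up sentence are group and time rather than outcomes, no outcome-level follow-up is stated at all. In either case, a real effect on one subscale could be accompanied by claims on subscales that did not change, or a gain shared by both arms could be read as an effect of sport education.

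**Working it through.** **Inputs.** From the documents: two arms, three time points, four SIMS and three PPLI subscales, 16 classes, a required sample of 341, α = 0.05. Assumed, because the documents give no figure:
- 3 to 4 outcomes per MANOVA, with correlation 0.3–0.5 between outcomes;
- correlation 0.6 with baseline, and 0.6 or 0.76 between post-intervention and follow-up, so the two changes correlate (0.6 − 1.2 + 1)/0.8 = 0.5 or (0.76 − 1.2 + 1)/0.8 = 0.7;
- ICC 0, 0.01 or 0.05;
- one outcome truly shifted at both later time points by d = 0.25 or 0.5 SD of change.

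**The plan's own figure.** The SAP gives no number for the follow-up. The Protocol's 341 can be reproduced from a two-group MANOVA with six responses (noncentral F on 6 and 334 df, noncentrality 341 × 0.25² = 21.3, power 0.95). The Protocol names neither the test nor the number of responses, so the match is conditional. Here 341 supplies only degrees of freedom: 341 − 2 = 339.

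**Scheffé on group.** The critical value is (k − 1) × F(0.95; k − 1, 339). With k = 2 it is 1 × F(0.95; 1, 339) = 3.869, which equals the squared two-sided t value on 339 df. Nothing is adjusted. As a main-effect post hoc, it compares means averaged over time. With equal baselines and a true difference δ at both later time points, it sees (0 + δ + δ)/3 = 2δ/3, plus any chance baseline imbalance.

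**Scheffé on time.** The critical value is 2 × F(0.95; 2, 678) = 6.018 against 3.855 unadjusted, a per-contrast level of 0.0144. This does adjust, but the means are pooled over arms, so a gain common to both arms would be flagged.

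**Scheffé on interaction contrasts (not stated in the SAP).** Applying the same multiplier to the two between-arm contrasts of change answers the right question, but holds 0.05 for each outcome separately. With 2 to 3 unaffected outcomes, the bound is 4 × 0.0144 = 5.8% to 6 × 0.0144 = 8.6%.

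**What the omnibus gate protects.** With no true effect and no clustering, the gate opens in 4.5–5.6% of trials, which limits all later claims. Once one outcome is truly affected, the gate tends to open. If it always opens, 2 to 3 independent unaffected outcomes tested at 0.05 give 1 − 0.95² = 9.8% to 1 − 0.95³ = 14.3%.

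**Simulation.** 4,000 runs per setting, 336 students in 16 unpaired classes of 21. The first four rows give the chance of at least one false claim on an unaffected outcome, over both values of d:

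| Procedure | ICC 0 | ICC 0.01 | ICC 0.05 |
|---|---|---|---|
| Scheffé on group, after the gate | 5–13% | 7–19% | 21–40% |
| Scheffé on interaction contrasts, after the gate | 4–8% | 8–13% | 23–36% |
| Holm at student level, after the gate | 3–5% | 5.5–8.5% | 19–27% |
| Holm on class means, no gate | 3–5% | 3–5% | 3–4% |
| Omnibus rejection with no true effect | 4.5–5.6% | 10–12% | 38–46% |

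The ICC 0 column isolates the follow-up. There the group test gives 4.9–7.8% at d = 0.25 and 9.0–13.1% at d = 0.5. It finds the truly affected outcome in only 16–23% of trials at d = 0.25. The rise to the right comes from ignoring class: student-level Holm rises too, and class-mean Holm does not.

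**Price of adjustment.** Detection of the affected outcome at either later time point, by t tests on class means (14 df):

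| | Unadjusted | Holm, both time points in one family |
|---|---|---|
| d = 0.25, ICC 0 | 70–74% | 33–41% |
| d = 0.25, ICC 0.05 | 44–49% | 14–19% |
| d = 0.5, ICC 0 | over 99% | 95–98% |
| d = 0.5, ICC 0.05 | 93–95% | 66–75% |

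**The case against.** The strongest reply is that this is missing detail and not a wrong method. Scheffé can be built on interaction contrasts, where the excess over 5% is small, or across outcomes in the Roy-Bose form, which could control error across them. The gate holds error near 5% when nothing is affected. At d = 0.25 without clustering, even the group test is little above nominal.

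Much of this stands, and it keeps the point moderate. It does not remove it. The SAP states a purpose (group-by-time effects) and one method, and on either factor that it names the method does not serve the purpose. Neither version that would work is stated.

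A reader might infer more than the documents support, in four ways.
- That Scheffé itself produces false-claim rates of 20–40%. Those rates arise only at an assumed ICC of 0.05, with class ignored. Neither document gives an ICC.
- That the plan is to run one unadjusted group-by-time test per outcome. The SAP states no such test, so its error rates do not describe this plan.
- That the group comparison must average over time. That is the main-effect reading; the text also allows a comparison at each time point or on change.
- That adjustment across every subscale and time point is obligatory. The power figures show a real trade-off. Holm within each MANOVA also leaves the series uncontrolled: with an assumed 4 to 6 independent families, 1 − 0.95⁴ = 18.5% to 1 − 0.95⁶ = 26.5%.

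**Conclusion.** The point holds. As written, the follow-up does not identify which outcomes changed differently between arms. On group, Scheffé adjusts nothing; on time, it pools the arms. That part is algebra and needs no assumption.

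The size does rest on assumptions. With one of 3 to 4 outcomes affected and no clustering, a false claim on another outcome has a chance of about 5–13% (group test) or 4–8% (interaction contrasts), a moderate excess.

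The missing class term is a separate defect, and potentially the larger one. It inflates the omnibus test itself, to about 10–12% at ICC 0.01 and 38–46% at ICC 0.05. The sentence about type I error is therefore true at most of the omnibus test within one MANOVA, and only if the analysis respects the randomised classes.

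The follow-up should be corrected before subscale results are relied on. Confidence is medium, because the ICC, the correlations and the number of outcomes per MANOVA are not in the documents.

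**What to change.** 1. Replace the Scheffé sentence with between-arm contrasts of change from baseline, at post-intervention and at follow-up, for each dependent variable. Use standard errors that account for class, for example t tests on class means: 14 df for 16 unpaired classes, fewer if the lecturer and sport grouping is modelled.
2. List the MANOVAs and their dependent variables.
3. Limit the type I error sentence to the omnibus test within one MANOVA, conditional on the handling of class.
4. Choose and state one of two policies. Either adjust across outcomes (for example Holm, saying whether both time points are in one family and that error across the series is not controlled), or report subscale results as unadjusted and exploratory. The choice is the sponsor's. Under the unadjusted policy, an outcome with no effect can be flagged at one or other time point in up to 2 × 0.05 = 10% of trials.
5. If the analysis is already done, report the new contrasts as a revised analysis.

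The cost is SAP wording and a re-run, with no new data. The main downside is power under the adjusted policy: at d = 0.25 detection is roughly halved or worse. If the grouping by lecturer and sport amounts to eight pairs (7 df) and matching brings no gain in precision, Holm detection at d = 0.25 falls further, to 25–32% (ICC 0) and 12–15% (ICC 0.05). Matching could recover some of that.
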